9.5. Study size

9.5.1. Sample size for cohort design

The target sample size is 50,000 subjects in each cohort. The relative risk (RR) that would be detected with 80% power and alpha = 0.05 is given in Figure 3 versus the incidence rate in the (Cervarix) unexposed cohort. The detectable difference in incidence rate (= additional cases per 100,000 person-years) is also depicted.

(Method: Comparison of two independent proportions using a likelihood ratio test, PASS 2005)

Cohorts of 50,000 subjects each should allow detection, with 80% power, of a RR between 3.7 and 18.7 for the neuro-inflammatory NOAD (incidence rate between 10 and 1/100,000 person-years) and between 1.6 and 2.0 for other NOAD (incidence rate between 100 and 50/100,000 person-years).

Because of risk of lost to follow-up, the sample size is increased by approximately 30% in each cohort to approx. 65,000 subjects.

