9.7.1. Hypotheses

9.7.1.1. Hypotheses for the cohort analysis

Null hypothesis (H0): the incidence of neuroinflammatory/ophthalmic autoimmune diseases (other autoimmune diseases) in the exposed female cohort is equal to the incidence in the historical non-exposed female cohort (historical cohort).

Alternative hypothesis (H1): the incidence of neuroinflammatory/ophthalmic autoimmune diseases (other autoimmune diseases) in the exposed female cohort is different from the incidence in the historical unexposed female cohort (historical cohort).

These hypotheses will be tested separately for each of the two co-primary endpoints. No alpha adjustment will be done.

The same hypotheses will be tested between the two male cohorts.

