9.7.5. Analysis of co-primary endpoints

9.7.5.1. Cohort analysis

The primary analysis will compare the incidence rates of the primary outcomes of interest between the Cervarix exposed female cohort and the historical unexposed female cohort. Results will be presented as the incidence rate ratio and the incidence difference. Exposed person-time will be defined as the period between the reference date and the earliest of the following events:

- End of study period (defined as 12 months after the reference date);
- Date of de-enrolment from CPRD GOLD;
- Date of unspecified HPV vaccine or Gardasil or Cervarix for unexposed cohort;
- Date of first diagnosis of the outcome of interest.

Incidence rates for auto-immune diseases will be calculated by dividing the number of cases by person-time. A Poisson regression model will estimate the risk ratio and its 95% confidence interval. The Poisson model will include the number of cases in each cohort as the dependent variable, the exposure status as a binary independent variable, the age-group ([9-18],[18-25]) as a covariate, and the log-transformed total person-year as an offset.

Sensitivity analyses

Sensitivity analyses will be performed:

- Incidence rates for NOAD in the exposed cohort will be calculated after each dose by dividing the number of cases by the total person-time. Exposed person-time will be defined as the period between the date of the dose administration and the earliest of the following events:
 - End of risk period (defined as 6 months after each dose);
 - Date of the next Cervarix dose;
 - Date of de-enrolment from CPRD GOLD;

- Date of unspecified HPV vaccine or Gardasil;
- Date of first diagnosis of the outcome of interest.
- Separate analysis will be performed for subjects younger/older than 18 years.
- Analysis including possible confounding factors (if available): other vaccination, age, region, healthcare resource utilization, categorization will be determined based on the available data.
- In case of more than 5% of NOAD with unknown/incomplete date, a sensitivity analysis will be done including these events as occurring during the risk period. This imputation will be done for the four cohorts.
- The same comparison will be done between the two male cohorts. In case of significant difference between these two male cohorts, the primary analysis will be adjusted for time effect other than Cervarix (see Section 9.7.5.1 for the detailed statistical models).

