9.7.8. Statistical calculations

All the statistical calculations will be done in SAS 9.2 or higher.

All the statistical tests will be two-sided at alpha level of 0.05.

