9.7.9. Statistical models

9.7.9.1. Poisson regression

Poisson regression will be computed using the SAS GENMOD procedure. The dependent variable is the number of events (*Y*). The main model (Model 1) will include the exposure status (exposed (X=1) vs. non-exposed (X=0)) as a binary independent variable, the age-group ([9-18],[18-25]) as a covariate, and the log-transformed total person-time (*PY*) of each exposed and unexposed cohort as an offset.

116239 (EPI-HPV-040 VS UK) Protocol FDA - EMA PASS Final Version 1 $\ln(Y) = \beta_0 + \beta_1 X + \beta_2 Z + \ln(PY)^\circ$

Female cohort model:

The coefficients β_1 and β_2 are the coefficients associated to exposure effect and age-group, respectively. The risk ratio (exposed/unexposed) will be derived as the exponential of the coefficient associated with the exposure status and its 95% Wald confidence interval.

The SAS code is:

PROC GENMOD data=<filename>; MODEL Y= X Z / offset=Ln_PY dist=poisson link=log; RUN;

The same model will be run for comparing the two male cohorts (concurrent vs. historical)

Male cohort model:

 $\ln(Y) = \beta_{0'} + \beta_{1'} X + \beta_{2'} Z + \ln(PY)^{\circ}$

The coefficient $\beta_{l'}$ is the time effect (concurrent vs. historical) in males.

The exposure effect in females adjusted for temporal effect in males model will be:

 $\ln(Y) = \beta_0 + \beta_{11} X_1 + \beta_{12} X_2 + \beta_{13} X_3 + \beta_2 Z + \ln(PY)^{\circ}$

Where:

 X_1 is '1' for the exposed female cohort and '0' for the other cohorts;

 X_2 is '1' for the concurrent male cohort and '0' for other cohorts;

X₃ is '1' for the historical male cohort and '0' for the other cohort.

The Cervarix effect in females adjusted for the temporal effect in males will be computed as :

$$\beta_{1*} = \beta_{11} - (\beta_{12} - \beta_{13})$$

The SAS code is:

PROC GENMOD data=<filename>; Class X (ref=' 1'); MODEL Y= X Z / offset=Ln_PY dist=poisson link=log; Contrast "vaccine adjusted effect in Females" X 1 -1 +1// estimate=exp;; RUN;

Note: X=1 for the non-exposed female cohort, 2 for the exposed female cohort, 3 for concurrent male cohort, and 4 for the historical male cohort.

Sensitivity analysis: A Poisson regression model including, in addition to the exposure and the age-group, other covariates

- Region (class variable: 13 regions defined in CPRD)
- Vaccination during the year prior to reference data (2 classes: yes, no)

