9.9. Limitations of the research methods

Limitations and recommendations for the research methods

As mentioned previously, Cervarix vaccination administration was done in the UK in the schools and administration of Cervarix is not reported for all subjects in CPRD. The vaccination record in the CPRD GOLD may not be complete; if for a certain subject no vaccination code for Cervarix is registered, vaccination status is uncertain. Due to the potential for under-reporting of HPV vaccination, an unexposed historical cohort (before introduction of Cervarix in the UK) was chosen instead of an unexposed concurrent cohort.

116239 (EPI-HPV-040 VS UK) Protocol FDA - EMA PASS Final Version 1

Although, diagnosis and/or coding of auto-immune diseases could change over time. Moreover, a link with HES was recently implemented in CPRD GOLD since 2009. The HES data coverage period is actually longer than 2009: currently April 1997 to March 2012. As such, historical controls will have the potential to have linked data in the same way as the more recent exposed group. In order to assess the possible impact of changes in auto-immune diseases diagnosis/coding in CPRD GOLD and HES over time, two male cohorts will also be enrolled: a cohort concurrent to the exposed female cohort and a historical cohort selected at the same time period as the unexposed historical female cohort. However, it is recognized that incidence of auto-immune diseases might vary according to sex as well as according to the age group. These two cohorts will be useful to study potential change over time in CPRD GOLD due to recent access to HES data that might increase the number of auto-immune diseases coded in the database.

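### The calendar-time adjustment applies only if the male comparison is significant, so small to moderate recording trends would usually stay in the reported rate ratio

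*Protocol*

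**What the plan says.** Protocol 9.7.5.1 makes the primary comparison "between the Cervarix exposed female cohort and the historical unexposed female cohort". By 9.2.2 and 9.2.4, reference dates run from September 2008 to August 2010 in the exposed cohort and from September 2005 to August 2007 in the historical cohorts. The main Poisson model (9.7.9.1) contains exposure and age group, with no term for calendar period.

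Section 9.9 gives the reason for the male cohorts: "Although, diagnosis and/or coding of auto-immune diseases could change over time". For these cohorts 9.7.1.1 states "The same hypotheses will be tested between the two male cohorts", and 9.7.8 adds "All the statistical tests will be two-sided at alpha level of 0.05".

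The result of that test decides whether the adjustment is made: "In case of significant difference between these two male cohorts, the primary analysis will be adjusted for time effect other than Cervarix". The adjusted model is written out in 9.7.9.1: "The Cervarix effect in females adjusted for the temporal effect in males will be computed as" β11 − (β12 − β13), that is, the log female ratio minus the log male concurrent/historical ratio.

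The rule stands among the sensitivity analyses yet says that the primary analysis will be adjusted. For the models it refers to 9.7.5.1, which is its own section; they are in 9.7.9.1.

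**The concern.** In the female comparison nothing separates the vaccine from the calendar period. The male cohorts are the only between-cohort means of doing so. Making their use depend on p<0.05 treats a non-significant male result as evidence of no trend, which a test on a few dozen events, or a handful, cannot supply.

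A rise in recording that the male test misses stays in the female rate ratio and its interval, where it reads as a vaccine effect. A missed fall can hide a real effect. Both matter in a post-marketing safety study. The rule also lets a male p-value decide which estimate is the headline one.

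**Working it through.** **Inputs.** Section 9.5.1 states "The target sample size is 50,000 subjects in each cohort", enlarged to about 65,000 for losses. Follow-up is 12 months, so person-years are about equal to subjects. Incidences in 9.5.1 are 1-10/100,000 (neuroinflammatory) and 50-100/100,000 (other diseases). Tests are two-sided at 0.05, with Wald intervals from the Poisson model (9.7.9.1). The documents give no trend size, so 1.2- to 2-fold is assumed, equal in both sexes.

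**Step 1: the protocol's own figures.** A pooled two-proportion z test with 50,000 per cohort and 80% power gives detectable ratios of 3.72, 18.49, 1.64 and 1.96 at 10, 1, 100 and 50/100,000. Section 9.5.1 states 3.7, 18.7, 1.6 and 2.0, so its figures are reproduced closely. The male cohorts have the same planned size, so at the same incidences these are also the smallest time trends the male test finds with 80% power.

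**Step 2: chance that adjustment is triggered.** With m expected events in historical males and trend t, z = ln t / √(1/m + 1/(mt)), and the chance is about Φ(z − 1.96).
- 100/100,000, t = 1.3: m = 50; z = 0.262/√(1/50 + 1/65) = 0.262/0.188 = 1.39; Φ(−0.57) ≈ 28%.
- 50/100,000, t = 1.3: m = 25; z = 0.262/0.266 = 0.99; Φ(−0.97) ≈ 16%.
- Neuroinflammatory, males at 5-10/100,000 (m = 2.5-5): counts are too small for this formula. Poisson simulation with Wald tests gives 0.5-4% at t = 1.3 and 1-7% at t = 1.5.

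With 65,000 in every cohort and no losses, the pooled z test gives about 36% and 20% for the first two lines.

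**Step 3: trend at which adjustment becomes more likely than not** (pooled z, 65,000 to 50,000 per cohort):
- 100/100,000: 1.37-1.43
- 50/100,000: 1.55-1.64
- 10/100,000: 2.4-2.7

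A doubling in the other diseases is found in 82-99.7% of studies across 50-100/100,000.

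**Step 4: male rates in Table 1.** For ages about 10-19, type 1 diabetes 35.0 + inflammatory bowel disease 4.2 to 10.7 + thrombocytopenic purpura 2.1 to 2.6 + lupus 0.1 gives 41.4 to 48.4/100,000. Adding US rheumatoid arthritis (3.6) and the all-age Scottish thyroid figure (22) to the upper sum gives 74.0. At 45-75/100,000 a 1.3-fold trend triggers adjustment in 15-28% of studies and a 1.5-fold trend in 32-60%.

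**Step 5: false rejection with no vaccine effect** (simulation, 50,000 person-years per cohort, equal male and female rates):

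| Incidence, trend | Unadjusted | Rule as written | Always adjusted |
|---|---|---|---|
| 100/100,000, 1.0 | about 5% | 6% | 5% |
| 100/100,000, 1.3 | 28% | 23% | 5% |
| 100/100,000, 1.5 | 61% | 26% | 5% |
| 50/100,000, 1.3 | 16% | 16% | 5% |

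For the neuroinflammatory endpoint at trends of 1.3 to 1.5, the rule rejects in about 4-7%.

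**Step 6: masking.** With a true ratio of 1.6, a 30% fall in recording and 100/100,000, the effect is detected in 9% of studies unadjusted, 31% under the rule and 36% always adjusted.

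**Step 7: price of adjusting.** With f and m expected events per female and male cohort and no effects, the variance of the log ratio rises from 2/f to 2/f + 2/m, so the standard error grows by √(1 + f/m): √2 ≈ 1.4 if m = f, √3 ≈ 1.7 if m = f/2. Power at a ratio of 1.6 and 100/100,000 falls from 75% to 41% and 29% respectively.

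**The case against.** The rule is better than no adjustment. In Step 5 most of the excess rejection comes from the historical-control contrast, and the rule lowers it: 26% against 61% at a 50% trend. With no trend the two-step level is about 6%, so testing first costs about one percentage point. A reader might infer that the rule creates the false findings; the calculations do not support that.

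A reader might also conclude that the male-adjusted ratio should become primary because it holds 5%. It does so only if both sexes share the same proportional trend. Section 9.9 itself notes that incidence might vary by sex, and Table 1 shows large differences (lupus at ages 10-19: 0.1 in males, 2.3 in females). A 30% trend confined to males would make the adjusted test reject in 16% of studies with no vaccine effect. The loss of power is also considerable.

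Two further points stand. The self-controlled case series tests both co-primary endpoints within exposed women and avoids the three-year contrast, although it does not correct the cohort ratio. Section 9.9 also says that hospital data cover April 1997 to March 2012, which weakens hospital linkage as a source of trend; the same section nonetheless still allows for changes in diagnosis, coding and hospital-data access.

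None of this justifies withholding the adjusted estimate when the male test is non-significant.

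**Conclusion.** The concern holds in a limited form. The rule would usually leave small to moderate trends in the reported ratio: below about 1.4- to 1.6-fold for other diseases, depending on incidence, and up to more than 2-fold for the neuroinflammatory endpoint. It would usually catch a doubling in the other diseases. The documents therefore do not support saying that a trend of any size goes unadjusted.

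Nor does an uncorrected trend necessarily become a significant vaccine finding: at 30% and 100/100,000 the rule gives a non-significant result in 77% of studies. For the neuroinflammatory endpoint, at trends of 30-50%, the harm is an uncorrected point estimate and interval rather than inflated significance.

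These sizes rest on assumed trends common to both sexes and on the incidences in 9.5.1 and Table 1. Should-fix: the safeguard is already specified, and only the condition on its use is badly chosen.

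**What to change.** In 9.7.5.1, delete the condition that the male cohorts differ significantly. State that for both co-primary endpoints:
- the unadjusted female ratio is the primary estimate, whatever the male p-value;
- the male-adjusted ratio exp(β11 − (β12 − β13)) with its 95% confidence interval is always reported as a pre-specified sensitivity analysis;
- the male concurrent/historical ratio is shown beside it with its 95% confidence interval;
- the three are interpreted together with the self-controlled case series, and the shared-trend assumption is stated.

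Correct the cross-reference so that it points to 9.7.9.1.

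The cost is about one more row in the primary results table for each endpoint. The model, contrast and cohorts are already planned. Because the adjusted interval is wider, that estimate should support the primary result and not replace it.

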For the SCCS analysis, the incidence rates in the exposed cohort during the risk period will be compared with the incidence rates in the exposed cohort during the control period using a conditional Poisson regression model [Whitaker, 2006].

Analysis of individual disease could also be performed depending on the number of cases (at least 10 cases in both exposed and non-exposed cohorts for each defined risk period).

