9.7.6. Secondary endpoints

The new cases of individual autoimmune disease during the specific period (see Section 9.3.2) will be analysed by descriptive statistics per cohort. Incidence rate during the specific period will be computed per cohort for each individual disease as the total number of new cases divided by the total person-year as for the primary endpoint.

In case of more than 10 cases in the exposed female and unexposed female cohorts, a Poisson regression model will estimate the risk ratio and its 95% confidence interval. The Poisson model will include the number of cases in each cohort as the dependent variable, the exposure status as a binary independent variable and the log-transformed total person-year as an offset. Same analysis will be performed for the two male cohorts.

A SCCS analysis of individual disease will be carried out if there are at least 10 cases of disease in the exposed female cohort and during the total of the risk and the control period. The risk period of each disease is the disease specific period : 2 months, 6 months, or 1 year depending on the disease (see Section 9.3.2), the control period is, 22 months, 18 months, or 12 months, respectively. The risk and the control periods are separated by a 6-month buffer period.

These analyses will not be considered as confirmatory analysis.

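### Whether a disease-specific risk ratio is computed may depend on the comparator's case count, and Sections 9.7.5.1 and 9.7.6 state the rule differently

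*Protocol*

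**What the plan says.** Section 9.7.5.1 (Cohort analysis) says that individual diseases could also be analysed, subject to "at least 10 cases in both exposed and non-exposed cohorts for each defined risk period".

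Section 9.7.6 (Secondary endpoints) restates the condition in other terms: "In case of more than 10 cases in the exposed female and unexposed female cohorts, a Poisson regression model will estimate the risk ratio". The same analysis is to be run for the two male cohorts.

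Other disease-level outputs do not depend on the comparator:
- Section 9.7.6: "Incidence rate during the specific period will be computed per cohort for each individual disease", with no minimum count.
- Section 9.7.6, self-controlled case series (SCCS): "A SCCS analysis of individual disease will be carried out if there are at least 10 cases of disease in the exposed female cohort", counted over the risk and control periods together.
- Section 9.7.8.2: case numbers and proportions per cohort, and a listing of every case with exposure status.
- Section 9.7.9.3: scan statistics for individual diseases in each cohort.

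On the window, Section 9.7.6 states: "The risk period of each disease is the disease specific period : 2 months, 6 months, or 1 year depending on the disease". On status: "These analyses will not be considered as confirmatory analysis".

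**The concern.** The two statements of the rule conflict. Exactly 10 cases in each cohort passes Section 9.7.5.1 but, read per cohort, fails Section 9.7.6. If Section 9.7.6 means the two cohorts combined, a split of 15 vs 2 is analysed there and excluded by Section 9.7.5.1. With both sentences in the plan, the choice could be made after the counts are known.

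Read per cohort, which is what Section 9.7.5.1 says and the natural reading of Section 9.7.6, the rule also selects in the wrong direction for a safety study. A vaccine effect raises the exposed count and leaves the historical count unchanged. For a rare disease the rule therefore admits balanced results and excludes the strongly unbalanced ones that most need a ratio with an interval.

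**Working it through.** **1. The protocol's own figures.** Section 9.5.1 starts from "The target sample size is 50,000 subjects in each cohort", then "the sample size is increased by approximately 30% in each cohort to approx. 65,000 subjects". A two-sided 5% pooled test of two proportions with 50,000 per cohort and 80% power gives detectable relative risks of 3.72, 18.49, 1.96 and 1.64 at 10, 1, 50 and 100 per 100,000. The protocol states 3.7, 18.7, 2.0 and 1.6, so its figures are reproduced closely.

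**2. Background rate needed.** For a mean of 10 comparator cases in N subjects over a window of w years, rate = 10 / (N × w). With N = 65,000 to 50,000 this is about 15 to 20 per 100,000 per year for 12 months, 31 to 40 for 6 months and 92 to 120 for 2 months.

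**3. Expected historical female cases.** Mean = Table 1 female rate × w × N. The last column is the Poisson probability of at least 10 cases with N = 65,000 and complete follow-up.

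| Disease, window | Rate per 100,000 | Mean, N = 50,000 | Mean, N = 65,000 | P(≥10) |
|---|---|---|---|---|
| Guillain-Barré, 2 months | 1.1 (UK 15-24) | 0.09 | 0.12 | about 0 |
| ITP, 6 months | 4.9 (UK upper) | 1.2 | 1.6 | 0.000007 |
| MS, 1 year | 2.5 (US 9-26) | 1.3 | 1.6 | 0.000008 |
| MS, 1 year | 5.9 (UK 20-24) | 3.0 | 3.8 | 0.006 |
| Optic neuritis, 1 year | 3.9 (US 9-26) | 2.0 | 2.5 | 0.0003 |
| SLE, 1 year | 4.7 (UK 20-29) | 2.4 | 3.1 | 0.001 |
| IBD, 1 year | 11.0 (UK 10-19 upper) | 5.5 | 7.2 | 0.19 |
| Uveitis, 1 year | 11.9 (US 9-26) | 6.0 | 7.7 | 0.25 |
| RA, 1 year | 13.8 (US upper) | 6.9 | 9.0 | 0.41 |
| Thyroiditis, 1 year | 19.5 (US 10-17) | 9.8 | 12.7 | 0.81 |
| Type 1 diabetes, 1 year | 26.0 (UK 10-19) | 13.0 | 16.9 | 0.97 |

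Table 3 supports the younger age bands: 82,326 + 65,080 of 148,288 vaccinees (99.4%) are aged 11-20, and 866 are aged 21-25.

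**4. What is withheld.** With equal person-time, the exposed count given the total is binomial with probability 0.5 under no effect.
- 10 vs 0: p = 2 × 0.5^10 = 0.002. The lower limit of the proportion is 0.025^(1/10) = 0.69, so the lower limit of the ratio is 0.69 / 0.31 = 2.2.
- 15 vs 2: p = 2 × (136 + 17 + 1) / 2^17 = 0.002, lower limit 1.7.
- 40 vs 9: p < 0.0001, lower limit 2.1.

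A rule of 10 in each cohort excludes all three. For optic neuritis with a true ratio of 10 and 65,000 per cohort, an exact test would be significant in 99.6% of studies, while the rule would allow the ratio in 0.03%.

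**5. The SCCS route.** At 65,000, the probability of at least 10 exposed cases over risk plus control periods is 51% for MS (2.5) at ratio 5 and 98% at ratio 10; 94% for optic neuritis at ratio 5; 99% for SLE (4.7) at ratio 5; 39% for ITP (3.4) at ratio 5 and 91% at ratio 10; and about 0 for Guillain-Barré.

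**6. Comparison with the co-primary analysis.** The neuroinflammatory composite has no minimum count. Section 9.5.1 assumes 1 to 10 per 100,000 for it, which is 0.65 to 6.5 comparator cases in 65,000. A ratio is accepted there on counts that would bar one for a single disease.

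**The case against.** A reader might infer that a strong effect on a rare disease could never be estimated, or that the rule hides it. The protocol does not support either. Incidence is reported per cohort for every disease, cases are listed with exposure status, scan statistics are run, and the SCCS gate needs no comparator. A split of 15 vs 2 would be visible in the report. What is missing is the between-cohort ratio and its interval. The SCCS does not fully replace that ratio, because it contrasts two periods after vaccination and has no age term.

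A reader might also infer from Table 1 that only diabetes and thyroiditis could qualify. That depends on the age band and country. SLE at the US 9-26 rate of 10.3 has a mean of 6.7 (probability of at least 10 about 0.14), and at the upper US 18-25 rate of 19.2 a mean of 12.5. IBD at the UK 20-29 rate of 21.9 has a mean of 14.2. Type 1 diabetes at the UK 15-34 rate of 10.1 falls to 6.6. Table 1 gives no rate for several listed diseases, such as transverse myelitis and psoriatic arthritis, so nothing can be predicted for them.

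Three further points count for the protocol. The secondary objective is to describe incidence, which the ungated rates do. The analyses are labelled non-confirmatory. The planned Wald interval from a Poisson model (Section 9.7.9.1) behaves badly with few cases and fails with none in the comparator, so some restriction on that model is reasonable. This justifies limiting the Poisson model, but not omitting a ratio for which an exact interval exists.

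**Conclusion.** The point holds for the between-cohort risk ratio of individual diseases. Sections 9.7.5.1 and 9.7.6 conflict on the threshold, and the second leaves open whether the count is per cohort or combined. On the per-cohort reading, the ratio would very rarely be available for MS, optic neuritis, SLE (at UK rates), ITP over 6 months or Guillain-Barré over 2 months, whatever the exposed count. It would be uncertain for uveitis, RA and IBD, and usually available for thyroiditis and type 1 diabetes at the rates tabulated. Guillain-Barré over 2 months is too sparse under any rule, so the gate is not the only cause there.

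Assumptions: Table 1 rates apply to panel-confirmed cases in this cohort, counts are Poisson, person-time is equal and follow-up is complete. Loss to follow-up would lower the comparator counts further. The composite co-primary analyses are not affected.

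**What to change.** Use one rule in Sections 9.7.5.1 and 9.7.6, preferably with no gate on the comparator count. For each disease, report the exact conditional rate ratio with its 95% CI, which has a finite lower limit even when the comparator has no cases. Keep the Poisson model for diseases with enough cases, with a single threshold that says whether it applies per cohort.

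If a gate is kept, define it on the two female cohorts combined. A combined minimum of 10 still excludes a split such as 8 vs 0 (exact p = 0.008), which is a reason to prefer no gate.

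Apply the same rule to the two male cohorts and keep the non-confirmatory label. The cost is a change of wording, a few table rows and some wide intervals.
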